16.4 Quality Assurance

1. Procedures in place to ensure the validity and integrity of the data: Each site will be responsible for implementing management and oversight activities during the pre-initiation, implementation, and close-out phases. These activities will be conducted by local project management staff located at each site and aim to provide management support to the research team in order to ensure adherence to the protocol, SOPs, and regulatory requirements. The Lead Team will provide on-going monitoring of study progress and will hold regular study management meetings to monitor any emergent problems or ongoing problematic trends, and may additionally hold individual meetings with site staff in order to assist in resolving any site-specific problems that impact the study.

2. Procedures to guarantee the accuracy and completeness of the data during data collection, entry, transmission and analysis: Assessments programmed in REDCap will use validation rules, integrity checks, and hard stops as needed to ensure that data are as complete and accurate as possible. The RA will check any data collected by paper source for completeness.

16.5 Regulatory Issues

1. Reporting of adverse events (AEs) and serious adverse events (SAEs) to the IRB, NIDA, and the FDA: All study-defined SAEs will be reported to the participating site's IRB and NIDA within 72 hours of their discovery. This is a behavioral study and so FDA reporting is not required. All participant information will be de-identified when reporting SAEs. In a case where a reported SAE may be very severe and/or require a protocol amendment to be made, [name] may request an ad hoc review by the DSMB. All study-defined AEs and SAEs will be entered into a database that is de-identified and password protected to ensure confidentiality.
2. Reporting of IRB action to NIDA: All communications with and actions of the IRB will be kept in a regulatory binder specific for this study. Any protocol changes, amendments, or deviations will be submitted to the IRBs and NIDA and the IRB's actions will then be reported to NIDA. Any other IRB actions will be submitted to NIDA.
3. Report of changes or amendments to the protocol: All changes and amendments to the protocol will be submitted to the IRBs and NIDA. Only after IRB and NIDA approvals are granted will the changes and amendments be implemented.
4. Trial stopping rules: Individual study participants will be informed of their right to discontinue study participation at any time during the study. The PI may discontinue a participant from the trial if deemed clinically appropriate. NIDA has the right to discontinue the investigation at any time.
5. Disclosure of conflict of interest: The investigators have no conflicts of interest.

16.6 Trial Safety

1. Potential Risks and benefits for participants:

Risks:

- Breach of confidentiality: As with any study, there is a potential risk of loss of confidentiality. To maintain participant confidentiality, study records and data will be stored in compliance with the International Conference on Harmonization (ICH) guidelines. Participant-reported data will be collected through REDCap, which is HIPAA-compliant and 21 CFR Part 11- ready for audit trails for tracking data manipulation and exports. Emails or text messages between researchers and participants, used in retention efforts, will be deleted after information exchange. All data will reside on password-protected computers, with only the investigators and key members of the research team having access. A variety of other measures will be taken to protect confidentiality, including: We will 1) assign a unique ID number to each patient to label all components of the

protocol, instead of patient names, 2) restrict access to the key linking names and ID numbers to key staff and the PI at each site, 3) store any paper with data in a locked area. Participants will be told that agents of the IRB, and QA monitors will be allowed to inspect sections of their research records related to this study, if requested.

- **Emotional Discomfort:** The participants may experience some emotional discomfort from answering sensitive and/or personal questions. There is the possibility that the participant will feel bored.
- **TOME risks:** The education intervention has been found to be safe and efficacious in prior studies. Participants may experience embarrassment if they receive feedback about missing numerous questions about opioid-overdose and MOUD.

Benefits: The results of the present study are unlikely to have a direct substantial societal impact. However, promising results would be used in support of a larger trial to test the efficacy of TOME. The study participants may directly benefit from study participation in that they will receive information about risks for overdose, the signs of overdose, how to respond to an overdose, and factors that can reduce the risk of an overdose. The study participants may also benefit from receiving naloxone. Consequently, the risk/benefit ratio is favorable and conduct of the research well justified.

2. **Collection and management of AEs and SAEs:** In general, the risks associated with trials employing behavioral interventions are presumed minimal relative to those evaluating pharmacologic interventions. An adverse event (AE) for this trial testing a low risk, education intervention is defined as: 1. Suicidal ideation and 2. Homicidal ideation.

SAEs will only be reported for events related to an AE (e.g., hospitalization due to suicidal ideation, etc.). We will use FDA criteria for SAEs (i.e., an adverse event that results in any of the following outcomes: death, life threatening event, initial or prolonged hospitalization, disability, congenital anomaly, intervention to prevent permanent impairment or damage, or other significant medical event). The study staff will be trained to monitor for and report AEs and SAEs. Additionally, as applicable, sites will submit reporting of AEs/SAEs according to IRB requirements. Each of the sites has established practices for managing medical and psychiatric emergencies, and the study staff will continue to utilize these procedures. Treatment providers at each site will be responsible for monitoring participants for possible clinical deterioration or other problems, and for implementing appropriate courses of action.

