6.4.2 Participant Selection

6.4.2.1 *Inclusion Criteria*

Potential participants must be:

1. 18 years of age or older;
2. pregnant or be within 12 months postpartum;

3. enrolled in MOUD (either buprenorphine or methadone) at the study site or affiliated clinic where enrollment can be confirmed;
4. able to understand the study, and having understood, provide written informed consent in English

6.4.2.2 *Exclusion Criteria*

[figure not shown]
Potential participants must not:

1. have suicidal or homicidal ideation requiring immediate attention
2. be currently in jail, prison, or any inpatient overnight facility as required by court of law or have pending legal action

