7.3 Safety Measures of the Primary Objective

7.3.1 Adverse Events (AEs)

There are not specific guidelines for adverse event (AE) and serious adverse event (SAE) reporting for behavioral trials but it is important to assess for potential AEs that could result from exposure to a behavioral intervention.²⁶ TOME is a low-risk intervention but staff will assess for two AEs that would be of clinical import: 1. Suicidal ideation and 2. Homicidal ideation. Research suggests that using the FDA definition of SAEs (i.e., an adverse event that results in any of the following outcomes: death; life threatening; requires hospitalization, initial or prolonged; results in disability; congenital anomaly; requires intervention to prevent permanent impairment or damage; or other significant medical event) for behavioral trials with substance using populations does not produce meaningful safety information in that many SAEs are reported but none judged to be related to the intervention.²⁷ SAEs will only be reported for events related to a study-defined AE (e.g., hospitalization due to suicidal ideation, etc.).

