Mental Health Follow-up Assessment: This assessment must be completed by a qualified clinician if the participant endorses suicidality or homicidality in response to the AE assessment. The completion of the Mental Health Follow-up Assessment form requires direct evaluation of the participant for suicide/homicide risk by a qualified mental health professional according to the site's specific SOP. This evaluation will ideally take place prior to the participant leaving the study visit. For visits held via telemedicine or at an external location, research staff will contact a qualified clinician via phone to coordinate an assessment via telemedicine as quickly as possible; ideally this assessment will occur while the staff and participant are together at the external location.

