10.3 Analysis Plan

Each outcome measure will be analyzed for the intent-to-treat population. All statistical tests will be conducted at the 5% Type I error rate (two-sided). All regressions will use outcome as the response variable, treatment (TOME vs. Control) as the covariate of interest, and baseline outcome as a supporting covariate. Site and site-by-treatment will be initially included as supporting covariates and dropped if they are not significant. Baseline-Week-3 continuous outcomes such as the difference in MOUD knowledge will be tested using linear regressions. The Pearson Chi-Square test will be used to test for treatment group differences in AEs.

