11.16.2 Adverse Events (AEs)

There are not specific guidelines for adverse event (AE) and serious adverse event (SAE) reporting for behavioral trials but it is important to assess for potential AEs that could result from exposure to a behavioral intervention.²⁶ TOME is a low-risk intervention but staff will assess for two AEs that would be of clinical import: 1. Suicidal ideation and 2. Homicidal ideation. Research suggests that using the FDA definition of SAEs (i.e., an adverse event that results in any of the following outcomes: death; life threatening; requires hospitalization, initial or prolonged; results in disability; congenital anomaly; requires intervention to prevent permanent impairment or damage; or other significant medical event) for behavioral trials with substance using populations does not produce meaningful safety information in that many SAEs are reported but none judged to be related to the intervention.²⁷ SAEs will only be reported for events related to an AE (e.g., hospitalization due to suicidal ideation, etc.). The study staff will be trained to monitor for and report AEs and SAEs. Additionally, as applicable, sites will submit reporting of AEs/SAEs according to IRB requirements. Each of the sites has established practices for managing medical and psychiatric emergencies, and the study staff will continue to utilize these procedures. Treatment providers at each site will be responsible for monitoring participants for possible clinical deterioration or other problems, and for implementing appropriate courses of action.

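### The only between-arm safety test ignores baseline ideation, so ideation carried over from baseline is mixed with new ideation; stratifying on baseline status recovers power at little cost

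*Combined protocol and SAP*

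**What the plan says.** The AE is defined in three places, each time as ideation itself. Section 16.6 item 2: "An adverse event (AE) for this trial testing a low risk, education intervention is defined as: 1. Suicidal ideation and 2. Homicidal ideation". Section 11.16.2 (and 7.3.1 in the same terms): "staff will assess for two AEs that would be of clinical import: 1. Suicidal ideation and 2. Homicidal ideation". None of them requires the ideation to be new, or worse than at baseline. Section 7.3.1 gives the reason for collecting it: "it is important to assess for potential AEs that could result from exposure to a behavioral intervention".

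The exclusion criterion (6.4.2.2, repeated in 16.1.3) reaches only candidates who "have suicidal or homicidal ideation requiring immediate attention". Lesser ideation does not prevent randomization. Table 1 in 8.4 marks the PRISM-Suicide/Homicide form at the screening/baseline visit only, and adverse events at Week 3 only.

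The analysis is one sentence, in 10.3 and again in 16.3 item 4: "The Pearson Chi-Square test will be used to test for treatment group differences in AEs". The rule in the same paragraph that the baseline value enters as a covariate is written for regressions, so it does not cover this test. No other between-arm safety comparison is planned.

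**The concern.** The stated purpose is to find events that the intervention could have caused. As written, the counted event is any ideation reported at Week 3, including non-urgent ideation that was already there before randomization and has not changed. Such cases occur at the same expected rate in both arms. They add events, and so variance, without adding information about TOME. A real excess of new ideation then has to show against a larger background, and a reader of the AE table cannot tell which cases came after the intervention. This matters because section 6.5 and the benefits paragraph of 16.6 present the pilot as support for a larger trial, and its AE table would be the randomized safety evidence carried forward.

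The plan handles efficacy differently: every regression adjusts for the baseline value of its outcome.

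**Working it through.** **The plan's own figure.** The documents give no rate or power for the AE test. The only power statement is for the primary outcome (10.4): 120 randomized, 88% attending Week 3, means of 7.3 v 6.7. With n = 120 × 0.88 / 2 = 52.8 per arm and the quoted post-intervention SD of 1.1: 0.6 / (1.1 × √(2/52.8)) = 2.80; 2.80 − 1.96 = 0.84; Φ(0.84) = 80%. This reproduces, so about 53 per arm at Week 3 is the right base for the AE test.

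**Assumptions.** Every ideation rate below is assumed. Let *per* be the share whose baseline ideation persists at Week 3 (equal in both arms) and *new* the onset rate among the rest.

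- All ideation (planned count): per + (1 − per) × new
- New onset only: (1 − per) × new

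Power comes from exact enumeration of two binomials with 53 per arm, Pearson chi-square without continuity correction, critical value 3.841.

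**New onset 2% Control v 10% TOME.**

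| per | All ideation, Control v TOME | Risk ratio | Power, all ideation | Power, new onset only | Persisting / all expected AEs |
|---|---|---|---|---|---|
| 0% | 2.0% v 10.0% | 5.0 | 41% | 41% | none |
| 3% | 4.9% v 12.7% | 2.6 | 29% | 39% | about 3 of 9 |
| 5% | 6.9% v 14.5% | 2.1 | 24% | 39% | about 5 of 11 |
| 10% | 11.8% v 19.0% | 1.6 | 17% | 36% | about 11 of 16 |

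Example at 5%: Control 0.05 + 0.95 × 0.02 = 0.069; TOME 0.05 + 0.95 × 0.10 = 0.145; ratio 2.1. The mechanism shows in the rejection threshold: significance needs 4 TOME cases against 0 Control, but 8 against 2 and 13 against 5.

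**Smaller harms.** At 2% v 5%, power is 8%, 8% and 7% (all ideation) against 10%, 9% and 9% (new onset) at 3%, 5% and 10% persistence. At 2% v 4% with 5% persistence the order reverses: 6.1% against 5.5%.

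**Harm through persistence.** Suppose 20% have ideation at baseline, it persists in 25% (Control) v 75% (TOME), and new onset is 2% in both arms. All ideation: 0.20 × 0.25 + 0.80 × 0.02 = 6.6% v 0.20 × 0.75 + 0.80 × 0.02 = 16.6%, power 36%. New onset only: 1.6% in each arm, rejection 0.9%.

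**Stratifying instead of restricting.** Week 3 ideation of any kind, tested by Mantel-Haenszel (no continuity correction) in two strata, with and without baseline ideation, by simulation at 53 per arm:

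- 5% baseline ideation, all persisting, new onset 2% v 10%: 24% planned, 40% stratified.
- The persistence harm above: 36% planned, 52% stratified.
- No arm difference: rejection about 4.5%, so the size holds.

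When all baseline ideation persists, that stratum carries no information and the stratified test rests on new onset alone. The small reversal at 2% v 4% therefore carries over to it.

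**The case against.** **The instruments are not shown.** The wording and look-back period of the Week 3 AE form are not in the documents, and an Operations Manual is mentioned (11.2) but not included. If either limits the question to new ideation, there is no problem. This stands as a condition. The available text leans the other way: the clinician assessment in 7.5 "must be completed by a qualified clinician if the participant endorses suicidality or homicidality in response to the AE assessment", with no reference to baseline. The PRISM items are not shown either, and 7.4.1 ties that form's clinical trigger to current intent. The fix assumes that the form records ideation.

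**Persisting ideation can itself be a harm.** If ideation would have resolved under Control but persists under TOME, exposure caused that outcome. This stands fully. A reader might infer that the test should be limited to new or worsened ideation. The persistence example shows why not: the planned test has 36% power there and a new-onset test 0.9%. Judging worsening would also add a post-randomization decision in an open-label trial.

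**The absolute excess hardly changes.** It is 7.8, 7.6 and 7.2 points at 3%, 5% and 10% persistence, identical whether all ideation or only new onset is counted. The plan names no risk ratio. Correct: what is lost is precision, not the expected difference.

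**The scenario is extreme.** A fivefold rise in ideation after a 15-minute education session has no support in the documents, and 16.6 describes the education as safe in prior studies. This stands as a limit on importance. For small harms no version of the test is informative.

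**It could be done anyway.** Section 10.7 permits post-hoc use of baseline variables. That is optional and chosen after the fact, so it does not replace a stated analysis.

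**Conclusion.** The point holds as a minor improvement to the safety analysis. The plan's only between-arm safety test pools new with carried-over ideation although baseline screening is already scheduled. Under assumed new onset of 2% v 10%, persistence of 3% to 10% brings power down to 29% to 17%, from 41% with none persisting. Stratification restores it to about 40% at 5% persistence. Whatever the p-value, the planned comparison gives no table separating new from persisting cases.

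This depends on three things the documents do not settle: persistence above 0%, a Week 3 form that does not already restrict to new ideation, and a PRISM form that records ideation.

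Two stronger readings are not supported. A reader might infer that the comparison is biased; it is not, because randomization balances baseline ideation in expectation. A reader might also infer a gap in participant protection; there is none on this point, because endorsement at the Week 3 AE assessment already calls for a clinician's evaluation. The primary analysis is unaffected.

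**What to change.** Leave the AE definition in 7.3.1, 11.16.2 and 16.6 as it is. It has to stay broad because "SAEs will only be reported for events related to an AE", and study-defined SAEs go to the site's "IRB and NIDA within 72 hours of their discovery". Narrowing the definition could remove a hospitalization for pre-existing ideation from that reporting.

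Change 10.3 and 16.3 item 4 only:

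1. Tabulate baseline by Week 3 ideation status in each arm.
2. Test any Week 3 ideation between arms with a Mantel-Haenszel test stratified by baseline ideation status, using the exact version if counts are small, with the rule for that fixed in advance.
3. Show new-onset ideation among those without baseline ideation descriptively, without a separate test.

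Baseline status is fixed before randomization, so no open-label judgement is added. Repeating the PRISM items at Week 3 for the period since baseline would make the visits comparable, but is optional.

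The cost is a short passage in two sections and one more table, with no new data collection if the PRISM form records ideation. The optional repeat adds one mark in Table 1 and a few minutes per visit. As a protocol change it needs IRB and NIDA approval (16.5 item 3). If the Week 3 form already asks only about new ideation, one sentence saying so is enough.

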16.7 Trial Efficacy

1. **Plans for interim analysis of efficacy data:** There will be no interim analysis of efficacy data by the investigators.

16.8 DSM Plan Administration

1. **Responsibility for data and safety monitoring:** Site study staff will be responsible for the clinical management and safety monitoring of the study participants.

2. Frequency of DSM reviews: Breaches of confidentiality will be reviewed by study leadership in regularly scheduled meetings for the duration of the study.
3. Content of DSM report: The DSM report, which will be contained in the final study report, will include a brief description of the study and any changes made. Additionally, we will report baseline sociodemographic characteristics, including age and race of the participants screened and randomized. We will also report retention rates and the disposition for all study participants. Any quality assurance issues, regulatory issues, and breaches of confidentiality will be included in the report.

16.9 DSM Board (DSMB) Plan

The MOMs (CTN-0080) trial has a NIDA CTN DSMB that is responsible for conducting periodic reviews of accumulating safety, trial performance, and outcome data. Given the low risk associated with the TOME intervention and the brevity of the study time frame, a separate DSMB was not established for the TOME trial. Instead, should [name] feel the need for DSMB input (e.g., as the result of an AE or SAE etc.) he will request an ad hoc meeting with the MOMs DSMB.
